7.1. Primary Endpoints

The primary endpoint of the study is to achieve superiority of mesh over native tissue repair at 36 months as compared to baseline.

Success will be based on a composite of objective and subjective measures, and subjects will be considered a surgical success if each of the three criteria is met:

1. Objective success is achieved by the subject having an anatomic outcome defined as the leading edge of prolapse at or above the hymen in the operated compartment:
 - Anterior segment: Leading edge of anterior prolapse is at or above the hymen or POP-Q point Ba \leq 0.

- Apical segment: The vaginal apex does not descend more than one-half into the vaginal canal (i.e. POP-Q point C < -1/2 TVL) for multi-compartment prolapse or POPQ point C ≤ 0 for single compartment apical prolapse.
2. Subjective success is achieved if the patient denies symptoms of vaginal bulging per PFDI-20 question 3, answering “no” or “yes” but “Not at all” bothersome (<2).
 3. No retreatment for POP: no additional surgical treatment for POP in the segment(s) of the vagina treated at the index surgery or no pessary use since index surgery (i.e., ‘treated segment’ refer to the target compartment).

Additionally, a co-primary endpoint of the study is to achieve non-inferiority of mesh to native tissue repair for safety by comparing rates of serious device or serious procedure complications between baseline and the 36 month time point. Serious injury is defined per 21 CFR 803.3, i.e., life threatening, results in permanent impairment of a body function or permanent damage to a body structure, or injury or illness that requires medical or surgical intervention to preclude impairment of a body function or permanent damage to a body structure.

7.2. *Secondary Endpoints*

The secondary endpoints of the study include assessments of complications and subject reported outcomes:

1. Incidence of mesh erosion
2. Incidence of mesh exposure
3. Incidence of de novo dyspareunia
4. Improvement in subject-related outcomes at 36 months compared to Baseline ((pelvic floor symptoms (PFDI-20), QOL (PFIQ-7), sexual functioning (PISQ-12) TOMUS pain scale)
5. Assessment of subject’s level of improvement, measured by the Patient Global Impression of Improvement for Prolapse (PGI-I for Prolapse)
6. Absence of re-intervention and re-surgery for recurrence of POP, persistence of disease, or mesh exposure/erosion
7. Surgical success based on the following composite outcome:
 - a. Subjective success: patient denies symptoms of vaginal bulging per PFDI-20 question 3, answering “no” or “yes” but “Not at all” bothersome (<2)
 - b. Anatomic success (in the operated compartment):
 - Anterior Segment: No anterior prolapse at or beyond the hymen or POP-Q point Ba<0
 - Apical Segment: The vaginal apex does not descend more than one-half into the vaginal canal (i.e. POP-Q point C < 1/2 TVL) for multi-

compartment prolapse or POPQ point C < 0 for single compartment apical prolapse.

- c. No retreatment for POP: No additional surgical treatment for POP in the segment(s) of the vagina treated at the index surgery or no pessary use since index surgery
8. Incidence of the following device or procedure-related AEs: pelvic pain, infection, vaginal shortening, atypical vaginal discharge, neuromuscular problems, vaginal scarring, de novo vaginal bleeding, fistula formation and/or de novo voiding dysfunction

8. Study Design

This study is a prospective, non-randomized, parallel cohort, multi-center study conducted in partnership with the AUGS PFD Registry.

The primary endpoint will be assessed once all per protocol subjects have completed the 36 month study visit. All per protocol subjects will be followed to month 36, until study completion, or until discontinuation prior to month 36. All study procedures will be standardized for uniformity. Physicians will have to provide documentation of a minimum of 10 procedures (i.e., native tissue repair procedure or Uphold/Uphold LITE procedure) prior to participation in order to document competency and experience. Physician training, specialty, and site procedure location (such as outpatient in private-practice, institutional hospital, etc.) will be recorded.

All efforts will be made to ensure all follow-up anatomic measurements (POP-Q) will be assessed by a healthcare provider to reduce treating surgeon bias on outcomes after the index procedure. In the event the treating surgeon is the only qualified healthcare provider at the site trained in POP-Q assessments, the follow-up anatomic measurements will be performed by the treating surgeon.

All enrolled subjects will have an anterior and/or apical defect. Concomitant procedures to treat a secondary defect can occur (including an anterior repair, posterior repair, hysterectomy, or sling placement for stress urinary incontinence), per physician discretion. Sling placement may include a synthetic material yet a concomitant anterior repair or posterior repair cannot include a mesh implant. An anterior colporrhaphy may be required, if clinically necessary. All concomitant procedures performed will be recorded.

Subjects who undergo a medical intervention (surgical or non-surgical) to treat recurrence, persistence of POP, or a mesh or suture complication will be followed to month 36 from the initial study procedure.

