9.2. Inclusion Criteria

Subjects who meet all of the following criteria may be given consideration for inclusion in this clinical investigation, provided no exclusion criterion (see Section 9.3) is met.

1. Subject is female
2. Subject is ≥ 18 years of age
3. Subject has pelvic organ prolapse with the leading edge at or beyond the hymen. At or beyond the hymen is defined as POP-Q scores of $Ba \geq 0$ (for prolapse of the anterior compartment alone) or $C \geq 0$ (for prolapse of the Apical compartment alone) or $C \geq -1/2$ TVL and $Ba \geq 0$ (for multi-compartment prolapse that includes the anterior and apical compartments)
4. Subject reports of a bothersome bulge they can see or feel per PFDI-20, question 3 response of 2 or higher (i.e. responses of “somewhat”, “moderately”, or “quite a bit”)
5. Subject or subject’s legally authorized representative must be willing to provide written informed consent
6. Subject is willing and able to comply with the follow-up regimen

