12.1.1. Primary Endpoint

The primary endpoint is an assessment of improvement in pelvic organ prolapse severity at 36 months as compared to Baseline.

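### In single-compartment prolapse, a POP-Q value of exactly 0 both qualifies a woman for entry and counts as primary anatomic success, and no committed analysis shows how much this matters at 12 and 36 months

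*Combined protocol and SAP*

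**What the plan says.** Inclusion criterion 3 (section 9.2 and the synopsis) reads "Subject has pelvic organ prolapse with the leading edge at or beyond the hymen". It defines this as Ba ≥ 0 for anterior-only prolapse, C ≥ 0 for apical-only prolapse, and C ≥ −1/2 TVL together with Ba ≥ 0 when both compartments are involved. Inclusion criterion 4 requires a score of 2 or more on PFDI-20 question 3.

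The primary composite (section 7.1 and the synopsis) has three parts, all of which must be met. The anatomic part is an "anatomic outcome defined as the leading edge of prolapse at or above the hymen in the operated compartment": Ba ≤ 0 for the anterior segment, C ≤ 0 for apical-only prolapse, and C < −1/2 TVL for the apex in multi-compartment prolapse. The other parts are a question 3 score below 2 and no retreatment.

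Section 12.1.1 describes the endpoint in terms of change: "The primary endpoint is an assessment of improvement in pelvic organ prolapse severity at 36 months as compared to Baseline".

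Secondary endpoint 7 (section 7.2, repeated in 12.1.2) is a similar composite with strict limits: "Anterior Segment: No anterior prolapse at or beyond the hymen or POP-Q point Ba<0", and C < 0 for apical-only prolapse. Its multi-compartment apical limit is printed as C < 1/2 TVL, without the minus sign used in 7.1.

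Section 12.3.8 plans a 12-month interim analysis of the primary endpoint and some or all of the secondary endpoints. It includes an effectiveness non-inferiority test on the composite at −12%.

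**The concern.** An outcome threshold that includes the entry threshold lets an unchanged measurement count as success. For a woman who enters at 0 in the only affected compartment, the anatomic criterion can fail only if she gets worse. It cannot show that the repair produced no anatomic gain, although section 12.1.1 describes the endpoint as improvement from baseline.

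If the arms differ less in these women than in others, the overall difference is pulled toward zero. That works against the sponsor in the 36-month superiority test. It works in the sponsor's favour in the 12-month non-inferiority test, which the footnotes to 12.3.8 link to a premarket application. Most centres contribute to one arm only (8.2, 12.2.2), so the share of women at 0 may also differ between arms.

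**Working it through.** **The plan's own figure.** Section 12.1.1.2 assumes 70% and 85% success, two-sided 0.05 and 90% power. With unpooled variance:

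n = (1.960 + 1.282)² × (0.70 × 0.30 + 0.85 × 0.15) / 0.15² = 10.51 × 0.3375 / 0.0225 ≈ 157.6, so 158 per arm.

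This matches the plan and does not depend on the overlap.

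**Entry set against success set.**

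| Component | Entry (9.2) | Primary success (7.1) | Overlap |
|---|---|---|---|
| Anterior only | Ba ≥ 0 | Ba ≤ 0 | Ba = 0 |
| Apical only | C ≥ 0 | C ≤ 0 | C = 0 |
| Apex, multi-compartment | C ≥ −1/2 TVL | C < −1/2 TVL | none |
| Bulge, question 3 | ≥ 2 | < 2 | none |

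The overlap is one value in each single-compartment type. A multi-compartment woman at Ba = 0 passes the anterior limit at entry but fails the apical one. She is therefore not an anatomic success at entry, provided both segments are scored. The bulge row shows that no eligible woman meets the composite at entry.

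**Under strict limits.** With success at Ba < 0 and C < 0, both single-compartment overlaps are empty.

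**Whether secondary endpoint 7 already does this.** It does for Ba and for apical-only C. For multi-compartment prolapse its printed limit is much looser than 7.1. With an assumed TVL of 8 cm, C < 1/2 TVL means C < +4, while 7.1 requires C < −4. As printed, it is not the primary composite with the overlap removed.

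**What can be said about size.** Let r_M and r_N be the shares of the mesh and native tissue arms that were at 0 at entry, are still at 0 at follow-up, and are otherwise successes. Scoring them as failures changes the crude difference (mesh minus native) by −(r_M − r_N). The documents give neither share. As an illustration, let 5%, 10% or 20% of women be at 0 at entry and let 10% of those be still at 0 and otherwise successful. The reclassified share is then 0.10 × 5% = 0.5%, 0.10 × 10% = 1%, or 0.10 × 20% = 2%. At 2% the crude difference moves by at most 2 points, and only if all such women are in one arm. Both inputs are assumptions.

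**The case against.** The case for leaving the definition alone is substantial, and most of it stands.

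- **Success at 0 may be deliberate.** Section 11.5 describes recurrence as prolapse beyond the hymen with bulge symptoms, which fits counting 0 as success. That explains the success limit, but not why entry uses the same value.
- **A woman still at 0 must have lost her bothersome bulge and avoided retreatment.** This is correct, and it keeps the point to the anatomic component.
- **A strict composite is already analysed on the ITT population.** This is true of secondary endpoint 7 at 36 months. At the interim it is optional, and its printed apical limit differs from 7.1.
- **Baseline Ba and C are in the propensity score (12.2.3).** This helps, but quintile strata need not balance the share at exactly 0.
- **Enrolment ended in December 2016 (Table 10.1-1).** A new primary definition at this stage has a real cost. A rule that depended on baseline would also score two women differently in the same follow-up state. This is a good reason to leave the primary definition unchanged.

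A reader might infer a stated loss of power. Suppose a share q of all women are at 0 at entry and contribute no arm difference. The 15 points then become 15 × (1 − q): 14.25, 13.5 or 12.0 points for q = 5%, 10% or 20%. With mesh held at 85% and 158 per arm, power would fall from 90% to about 87%, 84% or 75%. The documents do not support this reading. Neither q nor the zero difference has a source in them. The 70% and 85% rates are stated for the composite, so the 15 points may already allow for such women. The result also depends on which arm is held fixed: at 12 points it is about 75% with mesh at 85% and 71% with native tissue at 70%. Stricter scoring would not recover that loss, because any dilution from mild baseline disease comes from eligibility.

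**Conclusion.** The overlap is real and narrow. It affects anterior-only women at Ba = 0 and apical-only women at C = 0. For them the anatomic component can be met with no anatomic change, and success rests on bulge resolution and no retreatment.

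The size cannot be derived from the documents. The direction is conditional: if these women show a smaller arm difference, the estimate moves toward no difference, which is anti-conservative for the 12-month non-inferiority test. The documents do not support concluding that women can be primary successes at entry, that multi-compartment women are affected (given that both segments are scored), or that the study is underpowered for this reason. What the plan lacks is a committed analysis showing whether the 12- and 36-month conclusions survive without the overlap. That is worth adding and does not justify redefining the primary endpoint.

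**What to change.** Keep the definition in 7.1 and make these additions.

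1. In 12.1.1.3 and 12.3.8.2, pre-specify as a sensitivity analysis the primary composite rescored for every woman with strict limits: Ba < 0; C < 0 for apical-only prolapse; C < −1/2 TVL for the apex in multi-compartment prolapse, as in 7.1. Use the same propensity-stratified interval as the primary analysis at each time point, and the −12% margin at the interim. Rescore the earlier visits that feed the imputation model in the same way.
2. Report by arm, at 12 and 36 months, the number of women at exactly 0 at baseline in the qualifying compartment, and the number of those still at 0 and counted as successes. These counts isolate the overlap. The strict rescoring alone does not, because it also changes the result for women who improved from above 0 to 0.
3. State in 7.1 that both segments must pass in multi-compartment prolapse.
4. Reconcile the C < 1/2 TVL printed in the synopsis, 7.2 and 12.1.2 with the limit in 7.1.

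The cost is one extra analysis at each time point from POP-Q values already scheduled at baseline and every follow-up visit (Table 11.1-1). Success rates will be slightly lower in both arms under the strict rule.

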In an update of surgical treatment of POP, McIntyre et al. (2010) discussed the potential benefits of mesh use. In the treatment of anterior prolapse, studies indicated that potential benefits of mesh include increased durability of repair and improved anatomic outcomes.⁵ In one study of 70 subjects using mesh, McIntyre reported three (4.28%) recurrences, mesh extrusion in five subjects (7.1%), and 48 (87.3%) subjects reporting complete subjective satisfaction with their surgery at a follow-up of 18-36 months.

Four recent single-arm studies involving use of a mesh device for treatment of prolapse and one to two year follow-up documented anatomical cure rates ranging from 88.5%-94%.^{6,7,2,10} Reported vaginal mesh erosion rates for anterior repair ranged from 3.2%-6.5%, with one study reporting 13% mesh erosion for posterior repair.⁶

According to seven prospective randomized studies possessing at least one year clinical follow up, all but one indicate an exceptional reduction in anatomic recurrences after soft polypropylene mesh when compared to anterior colporrhaphy, with comparable or favorable quality of life and sexual outcomes.^{3,13,14,15,16,17,12} Six of seven of these RCT's reported >50% reduction in the cystocele recurrence rate, and four of seven reported \geq 75% reduction in anatomic failures. Crude recurrence rates were reduced, in these studies, from a range of 28-45% (colporrhaphy) to 7-21% (mesh).

Uphold™ Lightweight Surgical Mesh (Uphold LITE) is an FDA 510(k) cleared mesh implant intended for tissue reinforcement and stabilization of fascial structures of the pelvic floor in vaginal wall prolapse, where surgical treatment is intended, either as mechanical support or bridging material for the fascial defect. Uphold was designed as a VMR that would limit mesh exposures by placement through a horizontal, inverted crescent vaginal incision near the urethrovesical junction. The amount of mesh is approximately 75% less than other kits and apical support is achieved via sacrospinous ligament fixation (SSLF). Use of synthetic mesh grafts in surgical repair of vaginal prolapse has been shown to significantly increase success rates and reduce recurrent prolapse.

5. Device Description

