The Uphold LITE Vaginal Support System is a sterile, single use device for transvaginal placement, consisting of one (1) Uphold LITE Synthetic Mesh Assembly and one (1) Capiro™ SLIM Suture Capturing Device. The mesh assembly is a light-weight knitted mesh that consists of undyed and dyed polypropylene and monofilament fiber (phthalocyanine blue, color index number 74160) with two integrated leg assemblies. The leg assemblies include a dart, lead, dilator, two leader loops and protective sleeve. The dart at the distal end of the leg assembly was designed to be placed into the carrier at the distal end of the Capiro SLIM Suture Capturing Device. The leg assembly was designed to facilitate the passage of the Uphold LITE Synthetic Mesh Assembly through bodily tissues for placement through sacrospinous ligament. One dilator is striped to differentiate each leg assembly (left/right).

6. Study Objectives

The primary objective is to evaluate clinical effectiveness of transvaginal mesh repair against traditional native tissue repair in women surgically treated for anterior and/or apical pelvic organ prolapse. Secondary objectives are to evaluate mesh-related complications and subject reported outcomes.

7. Study Endpoints

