8.2.1. Treatment and Control

The treatment device in this study is Uphold Lightweight Vaginal Support System with transvaginal mesh (i.e., Uphold LITE). Please refer to the Directions for Use document for device-specific information. The surgical procedure steps will be standardized, including suture type (delayed absorbable or permanent sutures). Physicians will be trained to the standardized procedure steps prior to the first study procedure being performed. Minor modifications to the standardization may be necessary based on a physician’s practice and patient care.

The control procedure in this study is traditional native tissue repair, which includes sacrospinous ligament fixation or uterosacral ligament suspension and/or colporrhaphy. The surgical procedure will be standardized, including suture type (delayed absorbable or permanent sutures). Sacrospinous ligament fixation may be performed if the uterosacral ligaments are deemed unusable due to scarring or inability to access.

9. Subject Selection

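### The anatomic criterion of the primary composite follows the compartment operated on, not the baseline prolapse, so the POP-Q points scored can differ between arms

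*Combined protocol and SAP*

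**What the plan says.** **Anatomic criterion.** Criterion 1 in Section 7.1 (and the synopsis) asks for the "leading edge of prolapse at or above the hymen in the operated compartment". Item 7b of the secondary endpoints (7.2, 12.1.2) is tied to the operated compartment in the same way. The anterior rule is Ba ≤ 0. The apical rule has two thresholds chosen by type of prolapse: C < −1/2 TVL "for multi-compartment prolapse or POPQ point C ≤ 0 for single compartment apical prolapse".

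**Retreatment criterion.** Criterion 3 requires "no additional surgical treatment for POP in the segment(s) of the vagina treated at the index surgery". A parenthesis then explains that the treated segment is meant to "refer to the target compartment". The documents use that term again in exclusions 9 and 10 but never define it. Item 7c of the secondary endpoints has no such parenthesis.

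**The two operations.** Control is "traditional native tissue repair, which includes sacrospinous ligament fixation or uterosacral ligament suspension and/or colporrhaphy" (8.2.1), so colporrhaphy alone is allowed. Section 4 says the device obtains apical support by sacrospinous fixation. Section 5 says the leg assembly helps the mesh pass "through bodily tissues for placement through sacrospinous ligament".

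**Who is enrolled.** Inclusion criterion 3 (9.2) has three categories: Ba ≥ 0 "for prolapse of the anterior compartment alone", apical prolapse alone, and anterior plus apical prolapse.

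**The concern.** An endpoint should be scored by a rule that can be applied without knowing which treatment was given. Here the compartments to be judged are fixed by the surgery, and the surgery differs by arm. Where control surgery leaves out a compartment that the mesh operation covers, a mesh patient has one more way to fail than a comparable control.

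The treatment difference would then mix the effect of the repair with a difference in scoring. The composite also supports the 12-month non-inferiority and superiority tests (12.3.8.1), so the same problem carries over. In addition, a programmer deriving the endpoint for a woman with anterior-only prolapse whose apex was operated on would have to invent an apical rule.

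**Working it through.** **1. Literal scoring by case.** This sets criterion 1 beside the inclusion categories and the permitted operations.

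| Baseline prolapse | Index operation | Scored under criterion 1 | Scored under a baseline rule |
|---|---|---|---|
| Anterior and apical | Uphold LITE, apex counted as operated | Ba ≤ 0 and C < −1/2 TVL | the same |
| Anterior and apical | Control: suspension plus colporrhaphy | Ba ≤ 0 and C < −1/2 TVL | the same |
| Anterior and apical | Control: colporrhaphy alone | Ba ≤ 0 only | Ba and C |
| Anterior only | Control: colporrhaphy alone | Ba ≤ 0 | Ba |
| Anterior only | Uphold LITE, apex counted as operated | Ba ≤ 0; apical threshold not given | Ba |

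The third row differs from the first for the same woman. The fifth row is undefined.

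**2. Does the adjustment help?** The propensity model (12.2.3) contains POP-Q C, Ba and Bp but not the compartment operated on. Balancing baseline anatomy does not change which points are scored at 36 months.

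**3. The plan's own sample size.** Inputs from 12.1.1.2: 70% versus 85%, two-sided 0.05, 90% power. With unpooled variance,

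n = [0.70×0.30 + 0.85×0.15] × (1.960 + 1.282)² / 0.15² = 0.3375 × 10.51 / 0.0225 = 157.7, rounded up to 158 per arm.

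This matches the plan (the pooled-variance form gives 161). Enrolment also reproduces from the 165-per-arm target in 8.1: 165/0.80 = 206.25, so 207 per arm and 414 in total. No stated number is wrong.

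**4. Illustration of size.** The documents supply neither input below; both are assumed.
- f: share of women scored on the apex only if they are in the mesh arm.
- q: share of otherwise successful women in that group who fail at the apex alone.

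Mesh success is p = 0.85 × (1 − f×q), with control left at 70%. With n = 165 per arm, d = p − 0.70 and p̄ the mean of the two rates,

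power = Φ{[d − 1.96√(2p̄(1−p̄)/n)] / √[(0.70×0.30 + p(1−p))/n]}.

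For f = 25% and q = 10%: p = 0.85 × 0.975 = 0.829, and power is 79.0%.

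| f | q | Mesh success | Points lost | Power |
|---|---|---|---|---|
| none | none | 85.0% | 0 | 90.7% |
| 10% | 2% | 84.8% | 0.2 | 90.0% |
| 10% | 5% | 84.6% | 0.4 | 88.8% |
| 25% | 10% | 82.9% | 2.1 | 79.0% |
| 50% | 10% | 80.8% | 4.3 | 62.1% |
| 50% | 20% | 76.5% | 8.5 | 26.5% |

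If both arms truly had 70% success, the shift against mesh would be 0.70×f×q, from 0.1 points (f = 10%, q = 2%) to 7.0 points (f = 50%, q = 20%).

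**The case against.** A reader might infer that every mesh patient faces a stricter endpoint. The documents do not support that, for these reasons.

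- **Apical operation in every mesh case.** This is inferred from Sections 4 and 5, which describe how the mesh is anchored. Section 12.3.5.4 foresees index treatment of the anterior wall alone in each treatment group. It gives no rule for assigning that label to a mesh case, so the point is open rather than settled.
- **Anterior-only prolapse.** Both apical thresholds are conditional on a prolapse type that this woman does not have. A natural reading is that she has no apical criterion in either arm. The text is silent, which is not the same as stricter for mesh.
- **Retreatment.** The parenthesis in primary criterion 3 may already make it equal across arms. Pessary use and bulge symptoms are not tied to any compartment, so a symptomatic apical failure counts in both arms. What remains is an undefined term, its absence from criterion 1, and the missing parenthesis in item 7c.
- **How often it arises.** Nothing says that women with an apical defect receive colporrhaphy alone. Section 8.2.1 standardises control surgery and names sacrospinous fixation for when the uterosacral ligaments are unusable, which suggests suspension is intended where the apex needs repair. With suspension plus colporrhaphy the criteria are identical. The affected share could be near zero, but the plan sets no limit on it.
- **The power figures.** The plan assumes 85% for its own composite. Nothing shows that this figure refers to a more lenient, baseline-defined endpoint, so subtracting a penalty from it is itself an assumption.
- **Timing.** Enrolment was completed in December 2016 and the current revision is dated February 2018. Redefining an endpoint this late in an open-label study, in a direction that may help the sponsor's device, invites suspicion of a data-driven change.

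The first five objections limit the claim, but they leave intact the multi-compartment contrast under a literal reading of criterion 1. The timing objection bears on how the change is made and is met by locking the rule early and reporting both versions.

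**Conclusion.** The point stands as a gap in the endpoint definition. Criterion 1 and secondary item 7b let the scored compartments follow from the treatment. Read literally, that makes the endpoint harder for a multi-compartment mesh patient than for a similar control given colporrhaphy alone. The apical rule for anterior-only prolapse with an operated apex is missing, and the term on which primary criterion 3 relies is undefined.

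A reader might also infer a risk of false success for mesh. The direction is the opposite: the asymmetry counts against mesh, so it costs power and comparability for the superiority test and makes 12-month non-inferiority harder to show.

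Its size cannot be derived from the documents. The illustrative range, 90.0% down to 26.5% power at 165 per arm, is too wide to serve as an estimate and rests wholly on the assumed f and q. The definitional gap does not depend on those figures.

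**What to change.** In the synopsis and Sections 7.1, 7.2 and 12.1.2:

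- Define the target compartment(s) for both arms from baseline POP-Q, using the categories of inclusion criterion 3. Anterior only: score Ba. Apical only: score C. Anterior and apical: score Ba and C.
- Apply this definition in primary criteria 1 and 3 and in secondary items 7b and 7c, whatever procedure was done. It then follows that anterior-only prolapse carries no apical criterion in either arm.
- Lock the rule before any comparative outcome analysis, including the 12-month interim. The outcome-blind propensity work in 12.2.2 is a suitable point.
- Report the operated-compartment version as a sensitivity analysis.

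**Cost.** Wording and one derivation rule. Table 11.1-1 already collects POP-Q and vaginal length at baseline and at each follow-up visit from Month 2, so no new data are needed.

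**Downside.** This is a late clarification of a primary endpoint in an open-label study. Control success may fall slightly where an apical prolapse was left unrepaired, and apical descent in anterior-only mesh patients would no longer count in the anatomic criterion.
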